| Key secondary endpoint(s) (safety)     | 
The following key safety secondary endpoint(s) will be evaluated in the mother:
 
Local and systemic reactogenicity and adverse events:
 
 
• Solicited injection site reactions following the vaccinations
 
• Solicited systemic adverse events following the vaccinations
 
• All other adverse events following the vaccinations
 
• Laboratory tests; urinalysis; vital signs (heart rate, blood pressure, oral body temperature); physical examinations
 
 
The following key safety secondary endpoint(s) will be evaluated in the baby:
 
 
• Gestational age; weight; length; head circumference; Apgar score at 1, 5 and 10 minutes
 
• Developmental milestones at 6 months of age
 
   |

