## 2.5 Rationale for the present clinical study

MVX0004 is a phase II placebo-controlled study. The 50 µg GBS-NN/NN2 vaccine will be administered to healthy pregnant women.

The study will be conducted in compliance with ICH GCP E6 (R2) and applicable regulatory requirements.

The overall purpose of the study is to determine how four investigated vaccination regimens affect the concentrations of IgG antibodies, against the four AlpN proteins, in cord blood, namely, the vaccination regimens of; two doses at 22- and 26-weeks GA, 22- and 30-weeks GA, 26- and 30-weeks GA, and a single dose at 26 weeks GA, all doses administered by intramuscular injection.

Potentially, vaccination from mid-second trimester may have clinical advantages. A time interval of 8 weeks between the two doses might improve the immunological response in the mother, resulting in higher antibody concentrations in the baby when compared to a 4-week dosing interval. To be able to administer 2 doses 8 weeks apart dosing earlier in pregnancy will be necessary. If the antibody concentrations are similar, it would indicate that a flexible dose interval of 4 to 8 weeks between doses would be effective allowing greater flexibility in dosing. Dosing earlier in pregnancy will also have a potential advantage in reducing GBS induced preterm delivery between 30- and 37-weeks GA. The immune response to a vaccination course where the first vaccination is administered at 22- to 24- weeks GA will result in higher concentrations of antibodies at 30-weeks GA than a vaccination course where the first vaccination is administered at 26- to 28-weeks GA, and therefore may provide protection against adverse outcomes of pregnancy. Efficacy is not being explored in the current study, which is designed to assess the immune response at delivery.

The immunogenicity and safety of 50 µg GBS-NN/NN2 administered according to the four vaccination regimens will be evaluated, comparing the concentrations of IgG specific to the four AlpN proteins (RibN, Alp1N, Alp2N and AlpCN) in cord blood at delivery/birth and adverse event profile comparisons between the groups.

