#### **Serious Adverse Event (SAE):**

An AE that at any dose:

- Results in death; **Fatal**
- Is **Life-threatening\***
- Requires inpatient **Hospitalisation or prolongation of existing hospitalisation**
- Results in **Persistent or significant disability or incapacity**
- Results in **Congenital anomaly or birth defect**
- Is **Medically important**

\*The term 'life-threatening' refers to an event in which the subject was at risk of death at the time of the event; it does not refer to an event, which hypothetically might have caused death if it had been more severe.

Scheduled hospitalisation periods that were planned before the subject was included in this study are not to be considered serious.

In order to evaluate the risk of the IMP to cause severe liver injury the following must always be reported as a SAE under the criterion important medical event: Any occurrences of AST or  $ALT \geq 3 \times ULN$  together with total bilirubin  $\geq 2 \times ULN$  and confirmed as a Hy's Law case.

Hy's Law:

AST or  $ALT \geq 3 \times ULN$  together with total bilirubin  $\geq 2 \times ULN$ , where no other reason (i.e., viral hepatitis), other than the study intervention, can be found to explain the combination of increases.

Medical judgement should be exercised in deciding whether an AE is serious in other situations. Medically important events that are not immediately life-threatening or do not result in death or hospitalisation but may jeopardise the subject or may require intervention to prevent one of the other outcomes listed in the definition above, should also be considered serious.

Examples of such events are intensive treatment in an emergency room or at home for allergic bronchospasm; blood dyscrasias or convulsions that do not result in hospitalisation.

Admissions to hospital for a normal birth or for an elective Caesarean section leading to a healthy, term birth will not be deemed a serious adverse event, unless deemed an emergency caesarean section, in which case the reason the Emergency Lower Segment Caesarean Section (LSCS) was required will be reported as SAE.

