**Figure 1 Flow of data for study**

### 7.3 Statistics

Details of the planned analyses will be described in the Statistical Analysis Plan (SAP), providing a detailed discussion of the analyses outlined below. Any deviations from the planned analyses will be described and justified in the final clinical study report. The SAP will be finalized before data base release and the subsequent unblinding.

All study data will be listed, and all endpoint data will be tabulated. All categorical data will be tabulated by frequency and percentage while all continuous data will be tabulated by arithmetic mean, standard deviation, and range. Data used for log-transformed analyses will also be tabulated by geometric mean and coefficient of variation. This will be relevant for the immunogenicity endpoints. Exposure to vaccinations and compliance with the vaccination schedule will be tabulated and listed. All statistical analyses will be adjusted by site, as randomisation is stratified.

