## 7.10 Analysis of safety (key secondary endpoint)

### 7.10.1 Adverse events

AEs relating to mothers (study subjects) will be coded using the latest available version of MedDRA. An overall summary table will be provided showing the number and percentage of subjects, within the SAF analysis set, with any:

- Treatment-emergent adverse event (TEAE)
- Severe TEAE
- Treatment-emergent SAE
- Vaccine related TEAE

- Vaccine related severe TEAE
- Treatment-emergent vaccine related SAE
- TEAE leading to withdrawal
- TEAE with outcome death

The frequencies of the following key secondary safety endpoints will be tabulated in descriptive frequency tables:

- Solicited injection site events following the vaccinations
- Solicited systemic AEs following the vaccinations
- All AEs following the vaccinations

Treatment emergent AEs will be tabulated by system organ class and preferred term and treatment using the latest MedDRA coding.

All treatment emergent events will be listed. Non-treatment emergent events (if any) will be listed separately.

AEs in babies will be analysed and presented similarly to AEs in mothers, described above.

With respect to the babies, the following set of safety information will likewise be tabulated in descriptive summary tables (BSA analysis set):

- Gestational age
- Weight
- Length
- Head circumference
- Apgar score at 1, 5 and 10 minutes
- Developmental milestones at 6 months of age

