## 4 Statistical analyses and presentation of data

### 4.1 General considerations and summary of analyses

Summary tables presenting immunogenicity data (mothers and babies alike) as well as AEs including solicited injection site events and systemic AEs following the vaccinations will be presented a) pooled across all countries/sites and b) by geographical location South Africa / Europe (DK+UK).

All data collected from all sites will be sent to and analysed at Larix. Unless otherwise specified, all statistical tests will be performed using a two-sided test at a 5% significance level. Results from analyses will be presented with estimates, 95% confidence intervals (CIs) and p-values. For log-transformed analyses, which might be relevant for immunogenicity endpoints, the anti-log transformation will be applied before presentation. These transformed data will also be tabulated by geometric mean and coefficient of variation. Exposure to vaccinations and compliance with the vaccination schedule will be tabulated and listed.

Numerical/continuous data will be presented in summary tables by number of subjects, arithmetic mean (geometric mean and coefficient of variation [CV] where applicable), median, standard deviation (SD), minimum and maximum (or range). Categorical data will be presented by frequency and percent of subjects as well as number of events, where applicable. All data will be listed (see section 9, Layout of the outputs), and all endpoint data will be tabulated.

As there are more than one observation per subject (both mothers and babies) over time, time-dependent visualizations and, if possible, corresponding time-dependent statistical tests and modelling are carried out.

Prior and concomitant medication will be coded after WHO Drug Dictionary. Medical history and adverse events will be coded using the latest available version of MedDRA.

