### 4.7.2 Adverse events and other safety assessments in babies.

AEs in babies will be analysed and presented similarly to AEs in mothers, described above.

With respect to the babies, the following set of safety information will likewise be tabulated for all relevant Visits (8, 9, 10, 11) in descriptive summary tables (BSA analysis set):

- Gestational age
- Weight

- Length
- Head circumference
- Apgar score at 1, 5 and 10 minutes
- Developmental milestones at 6 months of age

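### Gestational age at birth is a key secondary baby safety endpoint, but no preterm cut-off, count or group contrast is planned, so an excess of preterm births would not be readily visible

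*Protocol*

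**What the plan says.** - **Endpoint.** The protocol synopsis lists "Gestational age; weight; length; head circumference; Apgar score at 1, 5 and 10 minutes" as key secondary safety endpoints in the baby. Protocol 3.6 and SAP 1.1.2.2 repeat the list.
- **Analysis.** Protocol 7.10.1 says that "the following set of safety information will likewise be tabulated in descriptive summary tables (BSA analysis set"). SAP 4.7.2 has them "tabulated for all relevant Visits (8, 9, 10, 11) in descriptive summary tables (BSA analysis set"). Table 5 in SAP section 6 carries gestational age into the early analysis after Visit 8, again with no category.
- **General rule.** Under Protocol 7.3, "all continuous data will be tabulated by arithmetic mean, standard deviation, and range". SAP 4.1 gives the mean and adds "median, standard deviation (SD), minimum and maximum (or range").
- **Rationale.** Protocol 2.5 gives several reasons for earlier dosing. One is: "Dosing earlier in pregnancy will also have a potential advantage in reducing GBS induced preterm delivery between 30- and 37-weeks GA".
- **Adverse event route.** Protocol 6.1 exempts admission for a normal birth, and an elective caesarean "leading to a healthy, term birth will not be deemed a serious adverse event". It does not mention preterm birth. Protocol 6.3 does not include it among the events of special interest for babies.

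**The concern.** The key secondary objective is safety when vaccination may start at about 22 weeks. Protocol 2.5 says that one regimen will be chosen for phase III on the immunogenicity and safety results, with the early analysis informing that choice. For gestational age, the safety question is whether more babies are born early. That is a question about the lower tail of a skewed distribution. A mean, and still more a median, moves little when a few more births per hundred fall below 37 weeks.

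Without a prespecified count, a reader of the early analysis would have to build one from listings, or choose a cut-off after unblinding.

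**Working it through.** **The plan's own figure.** Neither document states a rate, spread or power for gestational age. The only power claim concerns seroprotection at 1 µg/mL (above 90%). It reproduces at 96.7% by exact enumeration of the Newcombe-Wilson rule (60 per group, rate 95.65%, margin 15 points, one-sided 5%). It does not bear on this point.

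**Inputs from the documents.** Groups 1 to 4 have 60 women each and Group 5 has 30 (Protocol Table 1). Groups 2 and 3 receive vaccine at 22 weeks; Groups 1 and 4 first receive it at 26 weeks.

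**Assumptions.** The preterm rate p is 5%, 8% or 10%, doubling to 2p. Two shapes were tried:
- Shape A: term births normal around 39.6 weeks (SD 1.15, limited to 37-42.5). Preterm births are triangular on 28-37 weeks with the peak at 37, so their mean is (28 + 37 + 37)/3 = 34.0.
- Shape B: term SD 1.2, preterm SD 2.0, with means 3 to 5 weeks apart.

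**Step 1: movement of mean and median.** When p doubles, the mean falls by p × (term mean − preterm mean). Under shape A the gap is 39.6 − 34.0 = 5.6 weeks.

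| Preterm rate | Fall in mean | Fall in median | SD, before to after |
|---|---|---|---|
| 5% to 10% | 0.05 × 5.6 = 0.28 wk (2.0 days) | 0.6 day | 1.7 to 2.1 wk |
| 8% to 16% | 0.08 × 5.6 = 0.45 wk (3.1 days) | 1.1 days | 2.0 to 2.5 wk |
| 10% to 20% | 0.10 × 5.6 = 0.56 wk (3.9 days) | 1.4 days | 2.1 to 2.6 wk |

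Under shape B the mean falls between 0.05 × 3 = 0.15 week (1.1 days) and 0.10 × 5 = 0.50 week (3.5 days). With a 4-week gap the median falls 0.6 to 1.4 days.

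**Step 2: the same change as a count.** In an arm of 60, a rise from 8% to 16% is about 5 preterm babies (4.8) against about 10 (9.6).

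**Step 3: proportion against mean, 120 v 120, shape A.** The standard error of the risk difference is √[p(1−p)/120 + 2p(1−2p)/120]. That of the mean difference is √[(SD₁² + SD₂²)/120].

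| Preterm rate | Proportion: difference / SE | Mean: difference / SE |
|---|---|---|
| 5% to 10% | 0.05/0.034 = 1.5 | 0.28/0.248 = 1.1 |
| 8% to 16% | 0.08/0.042 = 1.9 | 0.45/0.287 = 1.6 |
| 10% to 20% | 0.10/0.046 = 2.2 | 0.56/0.308 = 1.8 |

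**Step 4: width of the intervals.** Suppose 10% and 20% are observed exactly. The Wilson 95% limits are 13.8-28.0% for 24/120, 4.7-20.1% for 6/60, 5.8-16.7% for 12/120, 15.4-25.5% for 48/240 and 3.5-25.6% for 3/30. Newcombe's lower limit is d − √[(p₁−l₁)² + (u₂−p₂)²], and the upper limit is formed likewise. For a difference of 10 points:
- Groups 2+3 v Group 1 (24/120 v 6/60): −1.9 to 19.6 points
- Groups 2+3 v Groups 1+4 (24/120 v 12/120): 0.9 to 19.1 points
- Groups 1-4 v Group 5 (48/240 v 3/30): −6.3 to 18.6 points

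**The case against.** The plan is not blind to early births. SAP 4.1 reports the mean, SD, minimum and maximum as well as the median. Under shape A at 8% to 16%, with two arms of 60, the mean difference is 0.45/√[(1.96² + 2.45²)/60] = 1.1 standard errors. The worse arm would therefore show the lower mean about 87% of the time. Every baby's gestational age is listed, and SAP 4.4.1 tabulates it again by treatment group as demographics. All baby adverse events are collected for 28 days, a preterm admission is not expressly exempt from serious event reporting, and the data safety monitoring board reviews adverse events after 27 births. The key table shells are a separate document (SAP section 10) and may already hold a preterm row.

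Most of this stands, and it limits the point. A reader might infer that a doubling would go unseen, or would be reported as no difference. The documents do not support that: several planned outputs carry some of the information. A reader might also infer that early dosing is justified by preterm delivery. Protocol 2.5 names it as one potential advantage beside the dosing interval and flexibility, and says that efficacy is not being explored.

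What remains is that each route is partial. The minimum reflects one baby. In simulated arms of 60 its median is 31.4 weeks at 8% and 30.4 at 16%, with overlapping interquartile ranges (30.2-32.8 and 29.5-31.4). A listing is not a group summary. No text says that a preterm birth itself must be recorded as an adverse event, so capture by that route is undefined. The infant weight model in SAP 4.8 analyses change adjusted for birth weight, so it does not show early delivery.

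**Conclusion.** The point holds as a matter of visibility. The documents plan no preterm cut-off, proportion or contrast for a key secondary safety endpoint. Under assumed doublings from 5-10%, the planned summary would move by about 0.6 to 1.4 days in the median and 2 to 4 days in the mean (down to about 1 day if preterm births lie closer to term), against an SD of about 2 weeks. A count gives a modest gain in precision: about 1.5 to 2.2 standard errors against 1.1 to 1.8 for the mean at 120 v 120. It does not give a powered test.

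Two conditions apply. The rates and shapes are assumptions. The reading that gestational age is summarised only as a continuous value is inferred from the general rules, because the table shells were not available.

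Groups 2+3 v Groups 1+4 might be read as a clean comparison of starting at 22 against 26 weeks. It is randomised, but Group 4 receives one dose, so it mixes timing with number of doses. Groups 2+3 v Group 1 compares two-dose regimens only.

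**What to change.** In SAP 4.7.2 and Table 5, keep the continuous summary and add, on the BSA:

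1. The number and percentage of babies born before 37+0 weeks and before 34+0 weeks, by arm, derived from the recorded gestational age and not from adverse event coding.
2. Descriptive Newcombe risk differences with two-sided 95% intervals for:
   - Groups 2+3 v Group 1 (two doses, vaccine from 22 v 26 weeks)
   - Groups 2+3 v Groups 1+4, labelled as also differing in number of doses
   - Groups 1-4 v Group 5

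If the table shells already contain a preterm row, the SAP should say so and state the cut-off.

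The cost is one derived variable with two cut-offs and a few table rows. No new data are needed, and the SAP already uses the Newcombe method for its primary comparisons. The downside is that all the intervals will be wide, not only those against the 30-woman placebo group, so the results should be labelled descriptive.

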## 2 Introduction

### 2.1 Background Group B streptococcus (GBS) infection and disease

*Streptococcus agalactiae*, also referred to as Lancefield's group B Streptococcus (GBS), is a Gram-positive diplococcus that colonizes the gastrointestinal and genital tracts of up to 30% of women. Normally, a commensal it does not cause clinical problems for colonized women. However, in pregnant women who are colonized with GBS there is a significantly higher occurrence of postpartum fever and endometritis compared to women who are not colonised. GBS is the most common causes of life-threatening invasive bacterial infections in neonates and young infants. Infections can result in neonatal sepsis, pneumonia and meningitis, in infants living in diverse regions (Fluegge et al. 2006; Lin et al. 2018; Neto 2008; Rivera et al. 2015), and is associated with significant mortality and morbidity, including long-term neuro-developmental sequelae (Kobayashi et al. 2016). GBS is also associated with disease in adults particularly in the elderly and adults who are immunosuppressed. GBS is also a cause of mastitis and perinatal puerperal infections (Kobayashi et al. 2016; Nuccitelli, Rinaudo, and Maione 2015; Kvist et al. 2008; Pass, Gray, and Dillon 1982; Shet and Ferrieri 2004).

GBS infection in new-borns is usually classified as early-onset disease (EOD), occurring during the first 6 days of life and late-onset disease (LOD) occurring between day 7 to 89 days of life. It is estimated that 60–90% of EOD occurs on the first day of life following in-utero infection (Verani, McGee, and Schrag 2010). Ascending infection of the vagina leads to infection of the chorioamniotic membrane and infection of the amniotic fluid and subsequent transmission to the foetus via the bronchopulmonary tree leading to EOD manifest as respiratory distress and septicaemia. Late onset disease may be caused by nosocomial, horizontal transmission from mother to baby or by transmission through breast milk. In late-onset GBS disease, the GBS bacteria adhere to infant mucosal surfaces, gaining access to the blood stream and crossing the blood brain barrier, leading to meningitis, which is a more common presentation of LOD.

The global incidence per 1 000 live births of invasive GBS disease in infants <90 days of age was recently estimated to be 0.49 (Madrid et al. 2017), which is slightly lower than the previous estimate of 0.53 (95% confidence interval (CI) 0.44 – 0.62) with a case fatality ratio of 9.6% (Edmond et al. 2012).

In the USA, the incidence of EOD has declined significantly (>80%) since the early 1990s through effective execution of secondary preventative strategies, i.e., screening all women at 35 to 37 weeks gestation and administering intrapartum antibiotic prophylaxis (IAP) to women determined to be colonised. IAP require intravenous antibiotics administered for at least 4 hours before delivery.

Worldwide in 2015, it was estimated that there were 205,000 infants with early-onset disease and 114,000 with late-onset disease, leading to 90,000 deaths in infants. There were 33,000 cases of invasive GBS disease in pregnant or postpartum women, and 57,000 foetal infections/stillbirths (Seale, Bianchi-Jassir, et al. 2017).

It has been estimated that there are some 2.6 million stillbirths world-wide annually, and that GBS accounts for 1% of stillbirths in developed countries but as much as 4% in sub-Saharan African

countries. In Africa there are 1.1 million stillbirths a year; hence GBS could be responsible for 44,000 stillbirths (Seale, Blencowe, et al. 2017). In addition, maternal GBS colonization has been associated with preterm delivery (Bianchi-Jassir et al. 2017), but there are multiple confounding factors, and the incidence has not been determined.

In addition to the inability of IAP to completely eradicate EOD and prevent GBS-induced LOD, stillbirth and preterm labour, the widespread use of antibiotic prophylaxis in GBS prevention has been associated with the emergence of antibiotic resistance in GBS, and an increase in the number of neonatal infections with antibiotic resistant strains of other bacteria such as *E. coli*. Penicillin remains the preferred antibiotic prophylaxis, but clinical isolates with reduced sensitivity to penicillin due to mutations in penicillin-binding proteins have emerged over recent years (Kimura et al. 2008). An alarming finding is that the emerging patterns of mutations are identical to those observed for *S. pneumoniae* prior to the breakthrough of widespread true penicillin resistance for that pathogen (Dahesh et al. 2008; Nagano et al. 2009). Full breakthrough of penicillin resistance in GBS will lead to a dramatic increase in the incidences of EOD, potentially returning the world to pre-IAP levels, as well as creating a serious problem when having to treat such resistant infections. In addition, wide-spread resistance to antibiotics other than penicillin already exists in GBS isolates (CDC, 2010).

Prevention of GBS infections in new-born babies and finding a safe and efficacious alternative to current antibiotic prophylactic strategies, therefore, represent a large unmet medical need.

## 2.2 Rationale for GBS vaccination during pregnancy

A vaccine against GBS, for use in pregnant women, enabling passive transfer of high concentrations of neutralizing anti-GBS antibodies to the foetus, and persisting for the first 3-6 months after birth, when the babies are most at risk, seems the obvious choice to address such unmet medical need. An effective vaccine will significantly reduce the need for current antibiotic prophylaxis during childbirth and hence, reduce the risks associated with emerging antibiotic resistance. In addition to having an effect on EOD, a vaccine will also potentially have an effect on *in-utero* infections (depending on the timing of the vaccination), reducing the incidence of stillbirths and preterm deliveries caused by GBS, as well as reducing the incidence of LOD infections by inducing persistent circulating IgG antibodies in the infant; none of these adverse outcomes of pregnancy are prevented through current IAP therapy.

From the literature, there is an association between GBS urinary tract infections (UTIs) during pregnancy, and premature rupture of membranes (PROM), preterm delivery and chorioamnionitis (Thomsen, Mørup, and Hansen 1987; Anderson et al. 2007). The incidence of GBS UTI during pregnancy is in the range of 1 to 2% of all pregnancies, and some 20-40% of these pregnancies result in preterm deliveries (Thomsen, Mørup, and Hansen 1987), which negatively affect pregnancy outcomes and carry extensive healthcare and social costs. A vaccine administered in the second trimester, capable of preventing GBS induced PROM and preterm delivery, would prevent some 45,000 such cases annually in Europe and the US. The global burden of GBS infection leading to premature delivery has been estimated at up to 3.5 million cases per year (Seale, Bianchi-Jassir, et al. 2017).

In addition, mothers provide antibodies (IgG and IgA) to their newborn babies in breast milk. A vaccine that can induce secretory IgA active against GBS as well as IgG, may potentially provide longer duration of protection against infection through the transfer of antibodies, particularly IgA, in breast milk.

